10.4 Statistical Analysis of Safety Data

Data from all subjects who receive at least one dose of study drug will be incorporated into the final safety analysis.

Safety will be assessed primarily based on reported TEAEs. Clinically significant clinical laboratory abnormalities will be reported as AEs (i.e., either as PTAEs or TEAEs, depending on when they initiate or worsen). The incidence of TEAEs will be tabulated by Medical Dictionary for Regulatory Activities (MedDRA) system organ class and preferred term, and will be further categorized by treatment arm, severity, and assigned relationship to study drug. The incidence of PTAEs will be tabulated by MedDRA system organ class and preferred term, and will be further categorized by severity.

The incidence for each PTAE and TEAE will be provided as the total number of subjects that experienced the PTAE or TEAE, as well as the percentage of the population that this represents. If a PTAE or TEAE is reported more than once for a given subject, the greatest severity and the worst-case attribution will be presented in the summary tables.

TEAE rates across treatment arms will be analyzed using the chi square test or an exact binomial test (e.g., Suissa and Shuster, 1985).

PTAEs and TEAEs will be separately listed for individual subjects, along with information regarding onset and end dates, onset time where available, severity, seriousness, relationship to

study drug (only in the case of TEAEs), action taken, and outcome. Separate listings and tabular summaries of PTAEs and TEAEs that lead to withdrawal from the study will be generated. Separate listings and tabular summaries of serious PTAEs and serious TEAEs will also be generated.

Secondary safety assessments, including physical examination, body weight, vital signs, orthostatic hypotension evaluations, ECG, hematology, serum chemistry, and urinalysis will be listed and summarized. Descriptive statistics will be generated as appropriate (i.e., mean, median, range, and standard deviation for continuous data and frequency for categorical data). The clinical laboratory results will also be summarized with respect to laboratory normal ranges and absolute changes from baseline. Comparisons among treatment arms will be performed using chi-square, binomial, and logistic analyses for dichotomous variables (e.g. normal/abnormal) and analysis of covariance (ANCOVA) for continuous variables.

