**e. Pre-treatment adverse events (PTAEs)**

If there are no serious PTAEs or PTAEs that led to withdrawal, the respective protocol-specified tabular summaries will not be produced. The protocol-specified tabular summary of all PTAEs will be produced, regardless.

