Dropouts and subjects who had major violations of the protocol will be excluded. Major protocol violations will include missing more than 25% of scheduled doses of study drugs, and taking prohibited medications including any NSAIDs or calcium channel blockers (other than the study drugs).

All randomized subjects should receive their initial dose of study drugs in the clinic immediately following randomization.

**Safety population:** All randomized subjects who received at least one dose of study drug will be included in the safety population. Analysis of safety variables, demographic and screening/baseline characteristics, past and concomitant diseases, previous and concomitant medications, and treatment compliance and extent of exposure will be performed on the safety population.

**PK population:** All subjects that were enrolled at an Investigational Site that had UV-shielded lights **and** who had a blood sample drawn on Day 14, 24 hours  $\pm$  1 hour after receiving the final dose of study drugs, for the measurement of plasma amlodipine concentration. This population will be used to produce the summary tabulation, t-test analysis, and box-plot analysis of the non-transformed plasma amlodipine concentration values, as well as the summary tabulation and t-test analysis of the log-transformed values.

**Randomized population:** All randomized subjects. The Randomized population will be used to produce all listings, except screening failures and the listing of plasma amlodipine concentrations. The screening failures listing will use the Overall Trial population and the listing of plasma amlodipine concentrations will use all subjects that were enrolled at an Investigational Site that had UV-shielded lights. The Randomized population will also be used to produce a summary tabulation of subjects who completed the study and who discontinued the study after randomization, and the primary reason for discontinuation. The Randomized population will also be used to produce a summary tabulation of the number of subjects in the randomized population, the ITT population, the mITT population, the PP population, the safety population, and the PK population.

**Overall Trial population:** All patients screened. This population will be used to produce a listing of screening failures and a tabular summary of the number of patients at Initial Screening Visit, at Final Screening Visit, at Baseline, randomized, and at each remaining study visit.

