### **PTAE**

Any untoward medical occurrence that initiates or worsens after completion of the Initial Screening Visit procedures and before administration of the first dose of study drugs will be recorded as a PTAE.

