### **PTAE leading to withdrawal**

A PTAE leading to withdrawal is a PTAE listed as the reason for the subject not being randomized to treatment on the “Study Termination” CRF.

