## 7.9. Safety Analysis

### AEs

PTAEs and TEAEs will be presented separately.

All AE analyses will use the Safety population. The AE listings will use the Randomized population.

See section 6.4 for AE definitions. Refer to Section 1.3.9, bullet d for further detail regarding how the PI assignments of expectedness differed from the protocol-specified definition and how this will be handled.

A summary of TEAE categories [all TEAEs, treatment emergent SAEs, ADRs, oedema events, other PTs of interest, treatment emergent UAEs, TEAEs leading to discontinuation, and TEAEs leading to death] by number of events within the category and the number and percentage of patients experiencing an event in that category will be tabulated by treatment group. Differences between groups will be evaluated using Chi-square test or Fisher's exact test (if more than 20% of the cells in a contingency table have expected counts less than 5).

AEs will be coded using the MedDRA dictionary (version 19.1). The incidence of all TEAEs will be tabulated by SOC, PT, severity and patient identification. The number of events and the number and percentage of patients with at least one event will be presented. Subjects experiencing more than one TEAE within a given SOC category will be counted only once for that SOC. Similarly, subjects experiencing more than one TEAE fitting a given PT will be counted only once for that PT. If a PT is reported more than once for a given subject, the greatest severity will be presented in the summary table.

The severity of AEs were graded as 1, 2, 3, or 4 according to WHO Toxicity Criteria (see Appendix C of protocol), or if the AEs were not included in this toxicity grading scale, they were categorized as mild, moderate, or severe per the definitions in Section 8.1.2 of the protocol. To allow for tabular summaries of severity, AEs assigned as grade 1 or mild will be included under mild, AEs assigned as grade 2 or moderate will be included under moderate, and AEs assigned as grade 3 or 4 or severe will be included under severe. Mild, moderate, and severe row headers will be presented under each PT, except in the case where there were no AEs across all treatment groups fitting a severity classification for that PT, in which case that severity classification will not be included as a row under that PT.

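### Pre-treatment AEs leading to withdrawal are defined by non-randomisation but reported only for randomised subjects, so the outputs the protocol requires cannot contain anyone

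*SAP*

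**What the plan says.** **Collection.** SAP 6.4 covers the whole pre-dose period: an event that starts or gets worse "after completion of the Initial Screening Visit procedures and before administration of the first dose of study drugs will be recorded as a PTAE". That window contains the washout, when subjects come off their current blood pressure drug (SAP section 3; protocol section 3).

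**Required output.** Protocol 10.4 asks for PTAE incidence tables, for outputs on serious PTAEs, and for outputs on withdrawals: "Separate listings and tabular summaries of PTAEs and TEAEs that lead to withdrawal from the study will be generated".

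**Definition.** SAP 6.4: "A PTAE leading to withdrawal is a PTAE listed as the reason for the subject not being randomized to treatment".

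**Populations.** SAP 7.9: "All AE analyses will use the Safety population. The AE listings will use the Randomized population". SAP 4.1 defines the Safety population: "All randomized subjects who received at least one dose of study drug will be included in the safety population". It then restricts listings: "The Randomized population will be used to produce all listings, except screening failures and the listing of plasma amlodipine concentrations". The only population that includes every screened patient is the Overall Trial population, of which SAP 4.1 says: "This population will be used to produce a listing of screening failures and a tabular summary of the number of patients" at each stage. No adverse event output is attached to it.

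**Suppression.** SAP 1.3.9e: "If there are no serious PTAEs or PTAEs that led to withdrawal, the respective protocol-specified tabular summaries will not be produced". SAP 7.9 repeats the rule, but calls the first group PTAEs leading to discontinuation. The table of all PTAEs is to be produced in any case.

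**The concern.** PTAE monitoring exists because the trial takes treated hypertensive subjects off therapy for 10 to 14 days before the first dose. Protocol 8.1.4 names hypertensive crisis, myocardial infarction and stroke among the events that may be expected from the subjects' age and underlying conditions. Protocol 4.3 lists a PTAE among the reasons for withdrawal. A subject withdrawn for such an event during washout is never randomised, and the reporting populations leave out exactly that subject.

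What is at stake is the account the study report gives of harm during washout. A missing or empty withdrawal table could be read as a finding that no such event occurred, when the populations chosen would give the same result with or without events. The tables of all PTAEs and of serious PTAEs have a milder form of the same problem: they describe only subjects who came through washout and went on to be dosed.

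**Working it through.** No figure in the plan is involved, so the check is one of set membership.

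**Sets**

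- R = randomised subjects (SAP 4.1, Randomized population).
- S = randomised subjects with at least one dose (SAP 4.1, Safety population). S is a subset of R.
- W = subjects with a PTAE leading to withdrawal. By SAP 6.4 each was not randomised, so W lies wholly outside R.
- N = subjects who entered washout but were not randomised for any reason. W is a subset of N, and N lies outside R.

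**Each PTAE output in turn**

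1. *Table of PTAEs leading to withdrawal* (Safety population): W ∩ S is empty, so no subject can appear.
2. *Listing of PTAEs leading to withdrawal* (Randomized population): W ∩ R is empty, so no subject can appear.
3. *Tables of all PTAEs and of serious PTAEs* (Safety population): N ∩ S is empty. These tables can hold events, but only from subjects later randomised and dosed. A subject randomised but not dosed would be listed and not tabulated.
4. *Other PTAE listings* (Randomized population): N ∩ R is empty, so non-randomised subjects contribute nothing.

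**Whether another output fills the gap**

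- The screening-failure listing covers non-randomised subjects and may show a reason. The SAP does not specify coded term, severity, seriousness or outcome for it, and it is not a tabulation.
- The discontinuation summary in SAP 7.4 starts after randomisation, and its reason categories include TEAE but not PTAE.
- The visit counts in SAP 1.3.6 and 7.4 show how many subjects were lost between screening and randomisation, but no event information.

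**Effect of the suppression rule.** If the test for whether there are any such events is run on the Safety population, the answer is always no and the withdrawal table is dropped. If it is run on all screened subjects, the table could be called for, but SAP 7.9 would still fill it from a population with no eligible subject.

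**Are the data there?** Yes. Protocol 12.1 requires a CRF for every subject who consents and has screening procedures, and SAP 6.4 takes the PTAE reason for non-randomisation from the Study Termination CRF.

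**The case against.** The strongest reply is that the population follows the protocol. Protocol 10.4 opens by basing the final safety analysis on subjects who took at least one dose, and the safety objective concerns the combination given for 14 days. That is true, and part of the tension starts in the protocol. But the same section asks for outputs on PTAEs leading to withdrawal, and applying the dosed-subjects sentence to them makes them impossible. The protocol also does not limit listings to randomised subjects; SAP 1.3.6 adds that.

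Other points stand in part:

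- *The suppression rule does not name a population.* Correct. A reader might infer that the report would show no PTAE withdrawals whatever happened. The text does not go that far, because on its plain words the rule is not triggered if such an event occurred anywhere in the trial. The conflict over which population fills the table remains on either reading.
- *The terms differ.* SAP 7.9 tabulates PTAEs leading to discontinuation, while only PTAEs leading to withdrawal are defined. The wording needs aligning, but no separate definition rescues the table.
- *SAP Appendix B, the list of tables, was not in the text available for this review.* It might assign populations table by table. If it did so differently, it would contradict the body of the SAP.
- *Safety oversight continues.* Under protocol 8.1.7, serious PTAEs go to the pharmacovigilance officer within 24 hours and are reviewed by the investigator and the medical monitor. A reader might infer that serious washout events go unreported; they do not. The gap is in tabulation and listing.
- *Not every non-randomised subject was harmed.* Day 0 exclusions include subjects whose daytime systolic pressure was 135 mmHg or below and subjects whose pressure was too high (protocol 6.2). Such an exclusion is not in itself a PTAE.

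**Conclusion.** The contradiction holds on the SAP's own definitions. All PTAEs leading to withdrawal fall outside the populations used to report them, and other PTAEs in non-randomised subjects are left out of every PTAE table and AE listing. Only the withdrawal outputs are empty by construction; the others are incomplete.

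The number of subjects or events affected cannot be computed. A reader might try to size it by assuming that 20% to 50% of washed-out subjects were not randomised. With 105 randomised, that gives 105/(1 − 0.20) = 131, or 26 not randomised, up to 105/(1 − 0.50) = 210, or 105 not randomised. The documents give no basis for those percentages, and the result counts subjects rather than adverse events, so it should not be cited as the size of the problem.

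Primary, secondary, pharmacokinetic and treatment-emergent results do not change, and serious events are still reported for safety purposes. The severity is therefore should-fix: a stated rule gives a wrong safety output, but no conclusion about treatment depends on it. This rests on the body text of the SAP and on reading withdrawal and discontinuation of PTAEs as the same thing.

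**What to change.** - In SAP 4.1 and 7.9, base the PTAE tables and listings (all, serious, leading to withdrawal) on every subject in the Overall Trial population who completed the Initial Screening Visit and entered washout. Use that number as the denominator and show randomised and non-randomised subjects separately.
- In SAP 1.3.9e and 7.9, state that the rule for omitting empty tables is judged in that same population.
- Use one term, either withdrawal or discontinuation, for PTAEs throughout, with the SAP 6.4 definition attached to it.
- Add a line to SAP 1.3 reconciling this with the dosed-subjects sentence in protocol 10.4, and keep the Safety population for treatment-emergent events.

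The cost is edits to a few SAP sections, a population flag for entry into washout, and modest reprogramming of the PTAE tables and listings. No new data collection is called for, given the CRF rule in protocol 12.1. PTAEs precede study drug and enter no efficacy test, so making the change in a SAP finalised after unblinding carries no inferential risk.

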### **1.3.9. Safety analyses**

#### **a. Oedema events**

A safety table extracting the occurrences of oedema events, which include treatment emergent adverse events (TEAEs) with preferred terms (PTs) of oedema, oedema peripheral, peripheral swelling, swelling, and joint swelling, from the adverse events table will be produced. See Section 7.9 for further detail. The rates of oedema events for treatment arms 1 and 2 will be reported and compared using exact logistic regression, reporting the odds ratio. The Fisher's exact test will be run to compare the number of oedema events that occurred while on treatment (Day 0 to Day 14+1) and post-treatment (>Day 14+1) between treatment arms 1 and 2.

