### 3.1. Sample Size

The sample size was based on findings of the KIT-302-03-01 study, and on the hypothesis that the mean reduction in SBPday from baseline to Day 14 of subjects treated with amlodipine tablets (10 mg) and celecoxib capsules (200 mg) given together (arm 1) minus half the mean reduction in SBPday from Baseline to Day 14 of subjects treated with amlodipine tablets (10 mg) given alone (with matched celecoxib placebo) (arm 2) is at least 0.

Sample size was based on the formula

$$n = \left\lceil 2 \left( \frac{Z_{1-\alpha} + Z_{1-\beta}}{d} \right)^2 s^2 \right\rceil$$

Where:

$s$  is the SD (8.7)

$d$  is the anticipated mean difference (6.2)

$\alpha$  is the one-sided level of significance (0.025)

$1-\beta$  is the power, one-sided (80%)

$\lceil \rceil$  is the ceiling function

The margin was based on a mean reduction of 8.8 mmHg in SBPday for the amlodipine + placebo arm and a mean reduction of 10.6 mmHg for the amlodipine + celecoxib arm as seen in the previous study, KIT-302-03-01. To ensure that at least half the effect is maintained, a value of  $10.6 - 0.5(8.8) = 6.2$  mmHg should be set for  $d$ .

The SD was based on an 8.1 mmHg SD for the amlodipine + placebo arm and a 9.2 mmHg SD for the amlodipine + celecoxib arm in the previous study (KIT-302-03-01). The pooled SD for the power and sample size justification is 8.7 mmHg.

The final sample size was rounded up to allow for a loss to follow-up. The study selected a round number at least 10% larger than the number necessary to protect against potential subjects not fully participating in the entire trial.

Approximately 105 subjects were to be randomized. Therefore, a sufficient number of subjects were to be screened so as to achieve approximately 105 subjects entering the randomization phase (starting at Day 0).

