### **Oedema events**

An oedema event is any TEAE with a PT of oedema, oedema peripheral, peripheral swelling, swelling, or joint swelling.

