### **Count of AEs**

Two AEs with the same PT and classified in the same category (PTAE or TEAE) that do not overlap in date of occurrence will be considered as two different events when calculating the “number of events” in the tables.

Secondary safety variables will include physical examination, body weight, vital signs, orthostatic hypotension evaluations, ECG, hematology, serum chemistry, and urinalysis.

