### 7.3. General Methodology

Descriptive statistics will be provided for all variables in the summary tables by treatment group and overall (except where noted as treatment group only) according to the type of variable summarized.

Quantitative variables will be summarized by using n (sample size), arithmetic mean, SD, median and range (minimum and maximum).

Categorical variables will be summarized by using frequency distributions and percentages.

For the safety analyses, hypothesis testing will be carried out at the alpha = 0.05 level (two-sided) when comparing treatments. P-value will be rounded to three decimal places. Statistical significance will be declared if the rounded p-value will be less than or equal to 0.05.

All data collected in the CRF will be presented in the listings.

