Similar tabular summaries will be produced for each of the following: treatment emergent SAEs, ADRs, oedema events, other PTs of interest, treatment emergent UAEs, TEAEs leading to discontinuation, PTAEs, PTAEs leading to discontinuation, and pre-treatment SAEs. In the case of the latter two, the summaries will not be produced if there are no PTAEs leading to discontinuation or pre-treatment SAEs, respectively. For the ADR summary, if an ADR is reported more than once for a given subject, the worst-case attribution will be presented in the summary table.

A comparison of TEAE rates between the amlodipine + celecoxib and amlodipine + placebo arms will be performed using an exact logistic regression model with the TEAE ("1"=At least one TEAE occurred for the patient; "0"=otherwise) as dependent variable and treatment (amlodipine + celecoxib and amlodipine + placebo) as fixed effects. The probability modeled will be TEAE="1". The number of patients and the number of patients considered in the model will be provided. The exact odds ratio of the fixed effects will be calculated (amlodipine + celecoxib and amlodipine + placebo) with the relative 95% CI and p-value.

The same model will be repeated by considering treatment-emergent SAE (“1”=At least one treatment-emergent SAE occurred for the patient; “0”=otherwise) as dependent variable, with the caveat that if no treatment-emergent SAEs are reported the table will not be produced.

The rates of oedema events between the amlodipine + celecoxib arm and the amlodipine + placebo arm will be compared using an exact logistic regression and reporting the odds ratio. Oedema event (1 = at least one TEAE with PT of oedema, oedema peripheral, peripheral swelling, swelling, or joint swelling occurring for the subject; 0 = otherwise) will be the dependent variable, and treatment (amlodipine + celecoxib and amlodipine + placebo) will be the fixed effects.

The Fisher’s exact test will be run to compare the number of oedema events that occurred while on treatment (Day 0 to Day 14+1) and post-treatment (>Day 14+1) between treatment arms 1 and 2 (amlodipine + celecoxib and amlodipine + placebo).

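### The Fisher test on on-treatment and post-treatment oedema counts events rather than subjects and has no defined 2x2 table, so its p-value can be too small if events repeat within subjects

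*SAP*

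**What the plan says.** SAP 7.9 (AEs) and SAP 1.3.9a plan the same analysis. Fisher's exact test is to "compare the number of oedema events that occurred while on treatment (Day 0 to Day 14+1", and likewise post-treatment, arm 1 against arm 2. Neither place says what forms the rows and columns of the table.

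The unit comes from SAP 6.4: "An oedema event is any TEAE with a PT of oedema, oedema peripheral, peripheral swelling, swelling, or joint swelling". Under Count of AEs, the same section says that two adverse events with one preferred term and in one category "that do not overlap in date of occurrence will be considered as two different events" when events are numbered in the tables.

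SAP 7.9 also plans an exact logistic regression of oedema in arms 1 and 2. That analysis has one binary outcome per subject: at least one qualifying term "occurring for the subject; 0 = otherwise) will be the dependent variable". It covers oedema overall and does not separate on-treatment from post-treatment onset.

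For safety analyses, SAP 7.3 says that "hypothesis testing will be carried out at the alpha = 0.05 level (two-sided").

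**The concern.** Fisher's exact test takes its reference distribution from independent units. Here the unit is the event, and two features of the SAP let one subject contribute more than one: five preferred terms are pooled, and separate episodes of the same term are separate events. The overlap rule applies within a preferred term, so concurrent peripheral oedema and joint swelling in one subject could also count twice. The once-per-subject rules in SAP 7.9 belong to the system organ class and preferred term tables. No such rule, and no adjustment for clustering, is stated for this test.

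At stake is a p-value that would be read against 0.05 while treating repeat events from a few subjects as separate evidence. No subject-level analysis of the on-/post-treatment split is planned beside it.

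**Working it through.** The documents give no sample size, power or p-value for this test, so there is no figure to reproduce. The check is a simulation with no true difference between arms.

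**Inputs from the documents**
- "Approximately 105 subjects were to be randomized" (SAP 3.1). At 3:3:1, arms 1 and 2 have 105 × 3/7 = 45 each. The final 6:6:1 ratio in SAP 3.2 would give 105 × 6/13 = 48.5, which is close.
- Two-sided test, rejection at p ≤ 0.05 (SAP 7.3).

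**Assumptions (not in the documents)**
- 12% of subjects affected in both arms, with 15.6% and 30% as alternatives. For scale, Protocol section 1 reports oedema rates of 8.2% and 15.6% in the prior trial.
- Events per affected subject = 1 + Poisson(λ), so the mean is 1 + λ.
- The first event is on treatment with probability 0.75 (0.70 in a second set of runs).
- Each later event copies the period of the first with probability ρ and is otherwise drawn afresh.

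Expected affected subjects are 2 × 45 × 0.12 = 10.8. At a mean of 2 events the table holds 21.6 counts, still from 10.8 subjects.

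**Type I error, 12% affected, all of a subject's events in one period (ρ = 1)**

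| Mean events per affected subject | Arm × period, 0.75 on treatment | Arm × period, 0.70 on treatment | On-treatment events over 45 subjects, 0.75 | Subjects with any on-treatment event, 0.75 |
|---|---|---|---|---|
| 1 | 0.011 | 0.011 | 0.017 | 0.017 |
| 1.25 | 0.035 | not run | 0.060 | 0.017 |
| 1.5 | 0.068 | 0.077 | 0.107 | 0.017 |
| 2 | 0.135 | 0.145 | 0.190 | 0.018 |
| 3 | 0.250 | 0.260 | 0.324 | 0.018 |

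Each setting used 6,000 to 20,000 simulated trials. In the fourth column, event counts are capped at 45. With 30% affected, the arm-by-period error is 0.070 at a mean of 1.25 and 0.281 at a mean of 3.

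**Effect of the period correlation (arm × period, 12% affected, 0.75 on treatment)**
- ρ = 0: 0.014 at a mean of 1.5 and 0.019 at 2. This is expected: given the number of events, independent periods are what Fisher's test assumes.
- ρ = 0.5: 0.039 and 0.061.
- ρ = 1: 0.071 and 0.134.

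Independent periods do not protect the other layout. With on-treatment events over number of subjects (0.70 on treatment), the error is still 0.076, 0.136 and 0.244 at means of 1.5, 2 and 3.

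**Direction.** At ρ = 1, rejections with the lower on-treatment share in arm 1 make up 0.036 of 0.071 (mean 1.5) and 0.062 of 0.134 (mean 2), about half.

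**Same subjects, different p (illustrative arm × period counts)**
- On/post 2/2 against 6/1 subjects: p = 0.49. Three events per subject, 6/6 against 18/3: p = 0.044.
- All events on treatment, 4/0 against 7/0: p = 1.0. Tripled, 12/0 against 21/0: p = 1.0.

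**After the fix.** With each subject counted once, on-treatment type I error is 0.017 to 0.026 over the 12%, 15.6% and 30% settings, whatever the number of events.

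**The case against.** The sentence just before the Fisher test in SAP 7.9 codes an oedema event as a per-subject yes/no variable, so the authors may have meant subjects. That is possible, but the variable carries no period, SAP 6.4 defines the event as a single TEAE, and SAP 7.9 distinguishes numbers of events from numbers of patients. The wording needs correction on either reading.

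Repeats may also be few. Treatment lasts 14 days, TEAE capture ends 14 days after the last dose, and same-term episodes count separately only if they do not overlap. With one event each, the test is conservative (0.011). This stands: the inflation is conditional and may not occur.

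A reader might infer that the test overstates the evidence for the sponsor's diuretic hypothesis. The documents do not support that. They do not tie this test to the hypothesis, which Protocol section 1 and SAP 1.1 discuss through oedema reporting rates by arm. The false rejections fall about equally on both sides. An arm-by-period table tests timing, not frequency, as the p = 1.0 examples show. The comparison of oedema rates is the subject-level regression, which this problem does not touch.

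**Conclusion.** The point holds as a defect of unit and specification. As written, the test counts events that the SAP allows to repeat within a subject, and its table is undefined. The p-value can be too small, in either direction, if events repeat and, in the arm-by-period layout, if a subject's events tend to share a period. Under full sharing with 12% affected, the nominal 0.05 is passed between means of 1.25 and 1.5 events per affected subject. Below that, or with independent periods in that layout, the level holds. The affected fraction, repeat rate and period correlation are all assumptions.

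The consequence is limited. This is one supplementary safety p-value outside the hierarchical testing procedure. No primary or secondary conclusion depends on it, and the exact logistic regression remains the main oedema comparison.

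**What to change.** In SAP 1.3.9a and SAP 7.9:

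- Count subjects with at least one oedema TEAE starting on treatment and, separately, subjects with at least one starting post-treatment. Use the Safety N of arms 1 and 2 as denominators.
- State the table: arm by subject with or without an event, one table per period.
- Apply Fisher's exact test to those subject counts.
- Report numbers of events descriptively, without a p-value.

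The cost is one reworded sentence in two places and a small programming change, using data already collected. SAP 1.5 lists the current version as finalised after unblinding, so the change should be recorded as a dated clarification with its reason.
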